3. Patient has sickle cell disease (SCD), including HbSS, HbSC, HbS β 0-thalassemia, or HbS β + -thalassemia, documented in their medical history by hemoglobin electrophoresis or genotyping.
4. If receiving hydroxyurea (HU), erythropoietin, L-glutamine, or prophylactic oral antibiotics, patient has had no change in regimen(s) (ie, drug and dose) for at least 8 weeks before the Randomization Visit and has no plans to change regimen(s) during the study. If receiving HU, patient must have been prescribed HU for at least 6 months prior to the Randomization Visit. (Note: Patient is not required to be taking medication[s] for SCD.)
Should the patient begin any new chronic treatment/therapy for SCD during the study or alter any current treatment/therapy for SCD during the study, the Sponsor Medical Monitor must be informed.
5. If receiving chronic medication(s) for hypertension, patient has had no change in regimen(s) (ie, drug and dose) for at least 8 weeks before the Randomization Visit and has no plans to change regimen(s) during the study.
6. Per medical history and/or patient recall, patient has had at least 1 and no more than 10 sickle cell-related pain crises in the 12 months before the Screening Visit and none occurring in the 4 weeks before the Randomization Visit.
For assessing study eligibility, an SCD-related pain crisis is defined as an acute episode of new-onset pain that lasts \geq 2 hours with no medically determined cause other than a vaso-occlusive event and requires presentation to a medical facility (eg, acute care setting, Emergency Department, urgent care clinic) and treatment with oral or parenteral opioids, parenteral nonsteroidal anti-inflammatory drugs, or other analgesics, prescribed by a healthcare provider.
7. Patient has clinically acceptable (per Investigator discretion) electrocardiogram (ECG) with QT interval corrected using Fridericia's formula (QTcF interval) <500 ms at the Screening Visit.
8. Patient has seated systolic blood pressure (BP) from 90 to 160 mmHg at the Screening Visit.
(Note: BP for eligibility will be the average of 3 measurements obtained with an

appropriately sized cuff at 2-minute intervals after the patient has been sitting quietly for ≥ 5 minutes.)

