### 3.5. Treatment Assignment

During the Run-in Period, all participants will receive placebo in a single-blind manner (Table 2).

Table 2. Dose Regimen During Single-blind Run-in Period

Dosage	Run-in (Day -17 or -14 to Day -1); QD Dose
placebo daily	1×matching placebo tablet
QD=once daily	

The Treatment Period is double blind and placebo controlled. Participants will be randomized through central randomization based on the protocol applicable at the time. The computer-generated randomization schedule will be prepared by an independent statistician not otherwise associated with the conduct of the study.

Under Protocol Amendment 3 or earlier, eligible participants will be stratified by hydroxyurea (HU) use and randomly assigned in a 1:1:1:1 ratio to 6 mg olinciguat, 4 mg olinciguat, 2 mg olinciguat, or placebo at Randomization Visit on Day 1 (Table 3).

Table 3. Dose Regimen by Treatment Period Week for Participants Randomized Under Amendment 3 and Earlier

Randomized Dose Level	Week 1=half dose		Weeks 2 to 12=full dose *	
	Dosage	QD Dose	Dosage	QD Dose
6 mg IW-1701	3 mg IW-1701 daily	1 × 3-mg IW-1701 tablet	6 mg IW-1701 daily	2 × 3-mg IW-1701 tablet
4 mg IW-1701	2 mg IW-1701 daily	1 × 2-mg IW-1701 tablet	4 mg IW-1701 daily	2 × 2-mg IW-1701 tablet
2 mg IW-1701	1 mg IW-1701 daily	1 × 1-mg IW-1701 tablet	2 mg IW-1701 daily	2 × 1-mg IW-1701 tablet
Placebo	Placebo daily	1 × matching placebo tablet	placebo daily	2 × matching placebo tablet

Under Amendment 4 and later, eligible participants will be stratified by HU use and randomly assigned in a 3:1 ratio to 18 mg olinciguat or placebo (Table 4).

Table 4. Dose Regimen by Treatment Period Week for Participants Randomized Under Amendment 4 and Later

Initial Dose Level (Day 1-Day 7)		Week 1 through Week 3 (Day 8-Day 28)		Week 4 through Week 12 (Day 29-Day 85)	
QD Dose	QD Dosage	QD Dose	QD Dosage	QD Dose	QD Dosage
6 mg IW-1701 daily	2×3-mg IW-1701 tablet	12 mg IW-1701 daily	4×3-mg IW-1701 tablet	18 mg IW-1701 daily	6×3-mg IW-1701 tablet
PBO daily	2×matching PBO tablet	PBO daily	4×matching PBO tablet	PBO daily	6×matching PBO tablet

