### 6.3. Sickle Cell Disease (SCD) History

SCD history will be listed and summarized by treatment group for the Safety Population. SCD history parameters include the time since SCD diagnosis (years), the type of SCD, number of vaso-occlusive crisis (VOCs) in the 12 months prior to the Screening Visit, the number of events (as defined in Eligibility Inclusion Criterion #6) requiring presentation to acute care clinic, the number of such events resulting in hospitalization, and the duration of current SCD treatment (months).

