### 8.1. Hemodynamics

The hemodynamic parameters are listed here:

- Change from Day 1 baseline in seated systolic and diastolic blood pressures (BPs) and pulse to predose at Weeks 1, 4, 8, and 12
- Change from Day 1 baseline in orthostatic systolic and diastolic BPs and pulse to predose at Weeks 1, 4, 8 and 12
- For each study visit (Day 1, Weeks 1, 4, 8, 12), change from predose to each postdose time point of the same visit for seated systolic BP, diastolic BP and pulse.

Details about BPs and pulse assessment are included in [Section 7.4](#). An orthostatic measurement is derived by subtracting the seated measurement from the standing measurement.

Descriptive statistics will be tabulated for each hemodynamic parameter by treatment group. In addition, an analysis of covariance (ANCOVA) model will be fitted with change from baseline as dependent variable, treatment group, and stratification factor (HU use) as fixed effects, and corresponding baseline value as covariate, at each visit/time point. Pairwise contrasts will be used to compare each olinciguat group with the placebo group. Least-squares means (LSMs) for each treatment group, LSM differences between each olinciguat group and the placebo group, their corresponding 2-sided 95% CIs, and p-values will be presented. Example SAS code for ANCOVA model is shown below:

```
Proc mixed data = analysis_data;
  class stratum trt;
  model chg = base stratum trt;
  lsmeans trt/ cl diff;
run;
```

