### 8.2. Vaso-occlusive Crisis (VOC)

#### 8.2.1. Primary Analysis of Exploratory VOC Parameters

Sickle cell-related pain crisis events will be documented as 'vaso-occlusive crises' (VOCs) on the AE eCRF page throughout the duration of the trial and adjudicated by an independent adjudicator. Only

This document is confidential.

adjudicated events that are deemed VOCs will be utilized in the endpoints defined below. An on-study sickle cell-related VOC is defined in [Section 5.2.5](#).

Acute chest syndrome, hepatic sequestration, splenic sequestration, priapism (each requiring a visit to a medical facility or documented telephone management) and death (except that due to suicide, accident, or other event clearly unrelated to the participant's medical condition) will also be considered VOCs, as well as subtypes of VOCs, for analysis purposes.

The exploratory VOC parameters are listed here:

- Time to first VOCs experienced during the Treatment Period, defined as (start date of VOC – the date of first dose of double-blind study drug + 1)
- Proportion of participants experiencing  $\geq 1$  VOC during the Treatment Period
- Annualized VOC rate during the Treatment Period, defined as  $365^*$  total number of events/ (last dose date – first dose date of double-blind study drug +1)

All 3 VOC parameters will be summarized by descriptive statistics by treatment group.

The time to first VOC will be summarized using Kaplan Meier method; the median event time (if appropriate) and 2-sided 95% CI for the median will be provided; 25% and 75% percentiles will also be presented. Additionally, the Kaplan Meier plots will be generated. For comparison between each olinciguat group and the corresponding placebo group, P-value will be generated from log-rank test.

Example SAS code for Kaplan Meier method is shown below:

```
Proc lifetest data=analysis_data;
  Time AVAL*CNSR(1);
  Strata trt;
Run;
```

For the proportion of participants experiencing  $\geq 1$  VOC (dichotomous endpoint), the proportions for each olinciguat treatment group and the corresponding placebo group will be compared using a Cochran-Mantel-Haenszel (CMH) test controlling for stratification factors (HU use). The difference in the proportions between each olinciguat group and the placebo group as well as the CMH estimates of odds ratio, risk difference, and p-values will be presented, along with the corresponding 2-sided 95% CIs.

Example SAS code for CMH model is listed as below:

```

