Proc freq data=analysis_data;
  Tables stratum*trt*resp/ cmh alpha=0.05;
Run;
```

The annualized VOC rate will be analyzed using a stratified Wilcoxon rank sum test with HU use as the stratifying factor. The associated P-value will be reported.

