### 8.2.2. Sensitivity Analysis of Annualized VOC Rate

In addition, the following sensitivity analysis will be conducted for annualized VOC rate, using Safety Population.

This document is confidential.

- Summary using descriptive statistics for participants enrolled under Protocol Amendment 4 or later, with PBO2, and 18 mg olinciguat (split into 6 mg, 12 mg, 18 mg groups based on the participant's last up-titration).

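### None of the exploratory VOC comparisons adjusts for the prior 12-month crisis count, so an imbalance in crisis history between arms would pass uncorrected into the observed contrast

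*SAP*

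**What the plan says.** Protocol inclusion criterion 6 (Amendment 5) requires that the "patient has had at least 1 and no more than 10 sickle cell-related pain crises in the 12 months before the Screening Visit". SAP 6.3 lists the "number of vaso-occlusive crisis (VOCs) in the 12 months prior to the Screening Visit" among the SCD history parameters and summarizes it by treatment group. Randomization is stratified by HU use alone. For Amendment 4 and later, SAP 3.5 says that "eligible participants will be stratified by HU use and randomly assigned in a 3:1 ratio to 18 mg olinciguat or placebo".

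SAP 8.2.1 compares three VOC parameters:

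- **Time to first VOC:** "P-value will be generated from log-rank test". The example code has treatment as its only strata variable, so HU use does not enter either.
- **Proportion with at least one VOC:** a CMH "test controlling for stratification factors (HU use").
- **Annualized rate:** "The annualized VOC rate will be analyzed using a stratified Wilcoxon rank sum test with HU use as the stratifying factor". Only the p-value is reported.

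The one VOC sensitivity analysis, in SAP 8.2.2, is descriptive: "Summary using descriptive statistics for participants enrolled under Protocol Amendment 4 or later", split by last up-titration. For continuous change-from-baseline endpoints, by contrast, the ANCOVA in SAP 8.1 takes the "corresponding baseline value as covariate, at each visit/time point". The MMRM in SAP 8.3.2 does the same.

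**The concern.** Crisis history is an obvious candidate predictor of on-study crises. The plan already collects it, and it already accepts baseline adjustment for continuous endpoints. The VOC comparisons rest on very small arms: 18 mg against about 12 concurrent placebo patients, and low-dose arms of about 10. If the arms differ in crisis history and history predicts the on-study rate, part of the observed VOC difference reflects who was enrolled rather than the drug. The planned tests cannot remove that part.

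The second set of comparisons in SAP section 8 adds a different problem. It sets every dose, including 18 mg, against placebo combined from all protocol versions. Placebo patients from Amendment 3 or earlier were never randomized against 18 mg, so a difference in crisis history there could be systematic rather than chance.

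**Working it through.** **Inputs from the documents.** About 88 patients: about 40 under Amendment 3 or earlier at 1:1:1:1, and about 48 under Amendment 4 and later at 3:1. Hence 40/4 = 10 per early arm, 48 × 3/4 = 36 on 18 mg, 48/4 = 12 on concurrent placebo, and 10 + 12 = 22 on pooled placebo. Treatment lasts about 12 weeks. The sample size was set outside statistical considerations, so there is no power figure to reproduce.

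**Assumptions not in the documents.** Prior counts are either uniform on 1 to 10 (mean 5.5, SD 2.87) or skewed low (mean 3.2, SD 2.26). The simulations use similar skewed distributions. On-study rate is proportional to the prior count raised to the power 1, 0.5 or 0. Patient heterogeneity is gamma with shape 2, and follow-up is 84 days.

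**Step 1: is the count used?** Log-rank no, CMH no, stratified Wilcoxon no, descriptive sensitivity analysis no: 0 of 4.

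**Step 2: chance imbalance, 36 versus 12.** SE of the difference in mean prior count = SD × √(1/36 + 1/12) = SD × 0.333.

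- Uniform: 2.87 × 0.333 = 0.96 crises per year, and 0.96/5.5 = 17% of the mean.
- Skewed: 2.26 × 0.333 = 0.75 crises per year, and 0.75/3.2 = 24% of the mean.

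By simulation, a difference of at least 1 crisis per year arises in 17% to 31% of trials at 36 versus 12. For a 10-patient low-dose arm against 22 placebo patients the figure is 23% to 37%, treating all as drawn from one population.

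**Step 3: effect of a one-SE imbalance on the contrast, if rate is proportional to prior count.** The share of the difference expected in the placebo arm is (1/12)/(1/12 + 1/36) = 0.75; the other 0.25 falls in the 18 mg arm. With a true rate ratio of 1.0 and the imbalance favouring drug:

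- Uniform: (5.5 − 0.25 × 0.96)/(5.5 + 0.75 × 0.96) = 5.26/6.22 = 0.85.
- Skewed: (3.2 − 0.25 × 0.75)/(3.2 + 0.75 × 0.75) = 3.01/3.76 = 0.80.

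**Step 4: simulation under no effect**, restricted to the roughly 1 in 6 trials in which prior count favours drug by more than one SE (quasi-Poisson model, 3,000 runs per scenario before that restriction; a repeat run agreed within simulation error):

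| Assumption | Median rate ratio, unadjusted | Adjusted | False result for drug (nominal 2.5%), unadjusted | Adjusted |
|---|---|---|---|---|
| Uniform, proportional | 0.80 | 1.01 | 10.3% | 3.9% |
| Skewed, proportional | 0.73 | 1.01 | 9.9% | 3.4% |
| Uniform, square root | 0.90 | 1.03 | 7.2% | 3.8% |
| Skewed, square root | 0.83 | 1.02 | 6.3% | 2.5% |
| Not prognostic | 1.00–1.02 | 1.00–1.01 | 2.5–2.8% | 2.3–3.0% |

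An equal imbalance the other way gave unadjusted ratios of 1.27 to 1.54 when the count was prognostic.

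**Step 5: averaged over all trials.** Type I error stays at about 4% to 6% with or without adjustment. At rate ratio 0.5 and full proportionality, quasi-Poisson power moves from 36% to 40% (uniform) or from 25% to 29% (skewed). At weaker dependence it changes by no more than about 2 points either way. At rate ratio 0.4 and full proportionality, the gain was 1 to 5 points. An illustrative HU-stratified Cox model at hazard ratio 0.5 (uniform counts) moved from 23% to 25% at full proportionality, and from 24% to 27% at square-root dependence. If the count is not prognostic, the SD of the log rate ratio rises only from 0.407 to 0.411 (uniform) or from 0.512 to 0.517 (skewed).

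**The case against.** The other side has real substance.

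- **VOC is not singled out.** A reader might infer that every other modelled PD endpoint is baseline-adjusted. That is not so: the Hb and HbF responder proportions and the 30% pain response use the same HU-only CMH test. Baseline adjustment in this SAP belongs to continuous change scores.
- **The count is an imperfect baseline.** It comes from medical history or recall and requires presentation to a facility. On-study VOCs also include telephone-managed episodes, acute chest syndrome, sequestration, priapism and certain deaths, and they are adjudicated. Protocol 3.8.8.6 itself notes that the pain-crisis definitions differ.
- **The spread is permitted, not observed.** The range of 1 to 10 is Amendment 5's. The criteria for the roughly 40 earlier patients are not shown, and the Amendment 3 schedule row reads Medical history where Amendments 4 and 5 read Medical/SCD history.
- **The average gain is small, and the tests are valid.** An imbalance of one crisis per year is possible rather than probable, and power is low either way.
- **CMH and stratified Wilcoxon take no continuous covariate.** Adjustment means adding regression models, not adding a term to the planned tests.
- **An imbalance would be visible.** SAP 6.3 tabulates the count by arm, and SAP section 2 allows supplementary analyses.

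All of this limits the size of the point and the form of the remedy, but the omission remains. Seeing an imbalance in a table does not correct for it, and an adjusted analysis chosen after seeing it carries less weight than one specified beforehand.

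**Conclusion.** The point holds at moderate weight. None of the VOC comparisons uses the prior crisis count. A one-SE chance imbalance at 36 versus 12 is about 0.75 to 0.96 crises per year under the assumed distributions. If the count is prognostic, that biases the result of the particular trial at hand: to a ratio of about 0.80 to 0.85 under proportionality, less under weaker dependence, and not at all if there is none. For 18 mg against pooled placebo, about 10 of the 22 placebo patients come from an earlier randomization, so balance in crisis history is not assured even in expectation.

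A reader might go further and infer that the planned tests are invalid, that type I error is inflated, or that adjustment would rescue the power. The documents and the calculations support none of these: error is held overall, and the average power gain is about 0 to 5 points. The VOC parameters are exploratory and the primary endpoint is TEAEs, so no primary conclusion is affected. The prior-count distribution and its prognostic strength are assumptions throughout.

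**What to change.** Keep the three planned tests. Add to SAP 8.2.2, before database lock, two prespecified covariate-adjusted analyses for both sets of comparisons in SAP section 8:

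1. A negative binomial or quasi-Poisson model for the number of adjudicated VOCs, with a log-exposure offset, treatment, HU use and log(prior 12-month VOC count). Report the rate ratio with its 95% CI.
2. A Cox model for time to first VOC, stratified by HU use, with treatment and the same covariate. This also brings in the stratification factor that the log-rank test leaves out.

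An adjusted logistic model for the proportion is optional if there are enough events. If any patient from an earlier amendment has a count of zero, use log(count + 1). State in the text that the prior count is narrower than the on-study definition, and that adjusting for it does not remove other differences between amendments in the pooled-placebo comparisons.

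The cost is a small amount of extra programming, one degree of freedom per model, and possible instability in the low-dose arms of about 10 patients. No new data collection is proposed.

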### 8.2.2. Sensitivity Analysis of Annualized VOC Rate

In addition, the following sensitivity analysis will be conducted for annualized VOC rate, using Safety Population.

This document is confidential.

- Summary using descriptive statistics for participants enrolled under Protocol Amendment 4 or later, with PBO2, and 18 mg olinciguat (split into 6 mg, 12 mg, 18 mg groups based on the participant's last up-titration).

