3.4.2 Removal of Patients from Therapy or Assessment

A patient will be considered to have completed the study after completing the Follow-up Visit.

A premature discontinuation will occur when a randomized patient ceases participation in the study prior to completing all study visits.

Patients will be informed that they are free to withdraw from the study at any time and for any reason.

The Investigator may remove a patient from the study if, in the Investigator's opinion, it is not in the best interest of the patient to continue the study. Patients may also be discontinued from the study by the Investigator or the Sponsor at any time for any reason, including the following:

- Adverse event(s)
- Protocol violation, including lack of compliance
- Lost to follow-up (an effort will be made to contact the patient, including sending a certified letter)
- Withdrawal of consent or assent by patient and/or parent permission of patient <18 years old (attempts should be made to determine the reason for withdrawal of consent if possible)
- Study termination by the Sponsor
- Other reasons (eg, administrative reasons)

A patient will be discontinued from study drug dosing for any of the following reasons:

- Female patient has a confirmed pregnancy (see Sections [3.8.7.2](#) and [3.8.8.9](#)).
- Patient has an AE of hemorrhage of Grade ≥ 2 per Common Terminology Criteria for Adverse Events (CTCAE) v4.03 (see Section [3.8.8.4](#)).
- Patient develops pulmonary edema.
- Patient has QTcF interval (QT interval corrected using Fridericia's formula) of >500 msec or an increase of >60 msec from baseline (ie, severity CTCAE Grade ≥ 3), based on machine-read calculations and confirmed with repeat ECG. Such QTcF prolongations should be recorded as AEs.
- Patient's treatment assignment becomes unblinded to the patient or the Investigator/site staff involved in the conduct of the study.

The Sponsor will be notified of any premature discontinuation. The date the patient is withdrawn from the study and the reason for discontinuation will be recorded on the study termination form of the electronic case report form (eCRF). Patients who discontinue from the study due to an AE will be followed until resolution of all of their AEs or until the unresolved AEs are judged by the Investigator to have stabilized.

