3.5.4.2 Uptitration (Week 1 and Week 4 Visits) during the Treatment Period

At the Week 1 (Day 8 ±1) Visit during the Treatment Period, patients will begin taking the uptitrated doses as noted in [Table 2](#) in the clinic *unless*: their seated systolic BP is <90 mmHg, their standing heart rate is >20 bpm greater than baseline, or they have unresolved AEs that, in the Investigator's opinion, should preclude uptitration.

- If a patient *does* uptitrate at the Week 1 Visit to 12 mg QD, the patient will be considered for uptitration to 18 mg QD at the Week 4 Visit (Day 29 ±3) based on the criteria listed above.
- If a patient *does not* uptitrate at the Week 1 Visit to 12 mg QD, the patient will remain on 6 mg QD and will be re-assessed at Week 4 for titration to 12 mg QD. If he/she is then uptitrated to 12 mg QD at Week 4, he/she will remain on 12 mg QD for the remainder of the study. If the patient does not meet criteria for uptitration to 12 mg QD at Week 4, he/she will remain at the 6-mg dose for the remainder of the study.

On the day after any uptitration or dose adjustment, preferably in the afternoon, the patient will receive a phone call for AE and concomitant medication assessments. Additional phone calls will be conducted per the [Schedule of Events](#).

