3.5.4.3 Dose Adjustments

It is recommended that the patient is evaluated in the clinic prior to any dose adjustment. According to his/her medical judgement, an Investigator may reduce a patient's dose as outlined below. Adjustments should be made, if possible, in consultation with the Medical Monitor.

- Patients who do not tolerate the initial 6-mg QD dose during Week 1 of the Treatment Period should be reduced to a 3-mg QD dose (ie, reduction by 1 tablet), with escalation to 6 mg QD considered at the Week 4 visit if they meet uptitration criteria (Section 3.5.4.2). Subsequent titration to 12 mg or higher will not be permitted for those patients.
- Patients who do not tolerate an uptitration to 12 or 18 mg QD should be reduced to their prior tolerated dose level (ie, 6 or 12 mg QD, respectively). Subsequent titration to a higher dose will not be permitted for those patients.
- If a patient develops any of the following **study drug-related TEAEs**, his/her dose will be reduced to his/her prior tolerated dose (or to 3 mg QD if receiving the initial 6 mg QD dose) and will not be retitrated to a higher dose:
 - 1 episode of Grade 3 vomiting (assessed per CTCAE v4.03) lasting >48 hours and not responsive to antiemetic therapy
 - 1 episode of Grade ≥3 syncope
 - 2 episodes of Grade 2 presyncope without orthostatic hypotension

On the day after any dose adjustment or uptitration, preferably in the afternoon, the patient will receive a phone call for AE and concomitant medication assessments. Additional phone calls will be conducted per the [Schedule of Events](#).

As noted above, with the exception of the lead-in dose during the first week, once a patient down-titrates, titration to a higher dose will not be permitted.

Investigators should notify the Medical Monitor of all decisions to reduce dose or to discontinue dosing on a per-patient basis.

See Section [3.4.2](#) for criteria triggering removal of individual patients from study drug dosing.

Note: Patients taking HU should be monitored for hematologic toxicities per the current prescribing information.

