3.8.8.5 Adverse Events of Special Interest (AESIs)

Based on the mechanism of action of sGC and anticipated vasodilation effects, the Sponsor will collect AESIs related to symptomatic or Grade ≥ 2 per NCI-CTCAE hypotensive events and/or tachycardia AEs. In addition, based on the prescribing information for riociguat (23, 24), bleeding events, pulmonary edema, and bone-related events, including fractures, will also be categorized as AESIs. The specific list of terms will be provided in the safety management plan and statistical analysis plan (SAP).

This classification means that although these events might be nonserious, they will be reported to the Sponsor per the timelines of SAEs, along with a causality assessment and an event narrative.

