#### 8.3.2. Sensitivity Analysis of Key Biomarkers

In addition, the following sensitivity analyses will be conducted for changes from baseline of Hb and HbF and proportions of biomarker responders specified above, using the Safety Population.

- Summary using descriptive statistics for participants enrolled under Protocol Amendment 4 or later, with PBO2, and 18 mg olinciguat (split into 6 mg, 12 mg, 18 mg groups based on the last uptitration).
- Mixed-effect model for repeated measures (MMRM) will be fitted with change from baseline as dependent variable, treatment group, visit, the interaction between treatment and visit and

This document is confidential.

stratification factor (HU use) as categorical variables, and corresponding baseline value as covariate. For each available visit, LSMs for each treatment group, LSM differences between each olinciguat group and the placebo group, their corresponding 2-sided 95% CIs, and p-values will be presented. An unstructured covariance matrix will be used to model the correlation among repeated measurements. MMRM models will use data available from the Weeks 1, 4, 8 and 12 visits.

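### Summaries of the 18 mg arm by dose step reached, beside unsplit placebo, are labelled sensitivity analyses; and the between-arm comparison of the annualized VOC rate yields only a P-value

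*SAP*

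**What the plan says.** **The split.** SAP 8.2.2 introduces its only item thus: "In addition, the following sensitivity analysis will be conducted for annualized VOC rate, using Safety Population". That item is a descriptive summary of Amendment 4 and later participants, "with PBO2, and 18 mg olinciguat (split into 6 mg, 12 mg, 18 mg groups based on the" participant's last up-titration. SAP 8.3.2 (Hb, HbF and responders) and 8.4.1.2 (SCD-SAF scores) each have a bullet with the 18 mg arm "split into 6 mg, 12 mg, 18 mg groups based on the last uptitration". Those two sections also list an MMRM by treatment group; 8.2.2 lists nothing else. PBO2 is one group in all three.

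**How the step is decided.** Protocol 3.5.4.2 allows uptitration at Week 1 and Week 4 unless seated systolic BP is below 90 mmHg, "their standing heart rate is >20 bpm greater than baseline, or they have unresolved AEs that" the Investigator thinks should preclude it. SAP 8.2.1 records VOCs on the AE page. Placebo follows the same tablet steps, up to "6×matching PBO tablet" (SAP 3.5, Table 4).

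**The rate.** SAP 8.2.1 defines it per participant as 365 × events / own dosing days. It gets descriptive statistics by group and a stratified Wilcoxon P-value. Time to first VOC gets Kaplan-Meier estimates, a CI for each group's median and a log-rank P-value. The proportion with a VOC gets an odds ratio and a risk difference with 95% CIs.

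**The concern.** A sensitivity analysis should ask whether the main result survives a change of assumption. This table changes the groups instead, forming them from something that happens after randomisation. A VOC unresolved at Day 8 or Day 29 can keep a participant off the next step, so participants with more VOCs tend to collect in the 6 and 12 mg columns and those with fewer in the 18 mg column. PBO2 keeps both kinds. A reader who sets the 18 mg column beside PBO2 compares a selected subset with a whole arm, under a heading that suggests a robustness check.

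Titration failure may also differ by arm for reasons unrelated to VOCs. The other two gates are haemodynamic, and Protocol 3.8.8.5 selects events of special interest "Based on the mechanism of action of sGC and anticipated vasodilation effects".

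The rate raises a separate point. A P-value gives no size of effect, and the descriptive statistics do not supply a stable one: the per-person mean can be driven by short dosing, and the median may be 0.

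**Working it through.** The plan gives no VOC rate, titration-failure rate or power figure (SAP 3.4 sets the sample size outside statistical considerations), so there is nothing to reproduce. From the documents: about 48 participants at 3:1, i.e. 36 vs 12; dosing to Day 85; uptitration at Days 8 and 29. All else is assumed.

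**1. Split, no drug effect, equal underlying VOC rates.** Let λ be VOCs per year. A VOC in the w days before a visit blocks uptitration with probability p, and no VOC ends dosing. With m = λw/365, expected VOCs in one window among participants not blocked are

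(1 − p)m / [1 − p(1 − e^−m)].

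Over 85 days, those reaching the top step expect λ(85 − 2w)/365 plus twice that; the whole arm expects 85λ/365.

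- λ = 2, w = 5, p = 0.5: m = 0.0274; window 0.0137/0.9865 = 0.0139; total 0.4110 + 0.0278 = 0.4387 against 0.4658, i.e. 5.8% lower.
- λ = 2, w = 7, p = 0.8: m = 0.0384; window 0.00767/0.9699 = 0.0079; total 0.3890 + 0.0158 = 0.4049 against 0.4658, i.e. 13.1% lower.

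Simulation adding 15% stopping for other reasons and 10% per visit not uptitrated for other reasons, with λ from 2 to 4, gives 6-14%.

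**2. Split, unequal underlying rates.** With gamma variation between participants (variance 1) the range is 8-23%. Example (3/year, 7 days, 80%): 7.6 / 4.5 / 2.4 per patient-year at 6 / 12 / 18 mg, against 3.0 for the whole arm.

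**3. When the gradient vanishes or reverses.** With no link between VOCs or underlying rate and titration, the three columns are 2.9 / 3.0 / 3.0 against 3.0. If participants with lower underlying rates fail titration on drug more often (10-20% per visit), the 18 mg column is 9-20% above the whole arm.

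**4. Per-person rate.** One VOC is 365/5 = 73 per year if dosing lasts 5 days and 365/85 = 4.3 over 85 days. Protocol 3.4.2 leaves stopping open: "Patients may also be discontinued from the study by the Investigator or the Sponsor at any time for any reason". At 3 VOCs/year, if 5-20% of VOCs end dosing, the mean of individual rates is 3.5-5.3 while the pooled rate is 2.8-3.0. If none do, they are 2.99 and 3.00.

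**5. Median.** The median of 12 is 0 when at least 7 have no VOC. With μ = 85λ/365, the chance of none over 85 days is e^−μ (equal rates): 0.63 at 2/year, 0.39 at 4/year. With variance 1 it is 1/(1 + μ): 0.68 and 0.52. Early stopping raises these somewhat. Simulated with 15% stopping, the PBO2 median is 0 in about 22-89% of trials and both arms' medians in about 4-88%.

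**6. Precision of a rate ratio.** Var(log RR) = 1/(36μ) + 1/(12μ) + k/36 + k/12, where k is the overdispersion.

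- 4/year, k = 0: μ = 0.932; variance 0.119; SE 0.345; limits a factor e^(1.96 × 0.345) = 1.97 either side.
- 2/year, k = 1: μ = 0.466; variance 0.239 + 0.111 = 0.350; SE 0.591; factor 3.19.

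Simulated model fits reached a factor of about 3.4.

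**The case against.** - **The whole-arm comparison is already planned.** SAP 8.2.2 is additional to 8.2.1, which summarises and tests the rate by treatment group, and SAP 8 names 18 mg against PBO2. This stands. A reader might infer that the split biases or replaces the tested comparison; it does neither. Final table columns may also be set in the TFL shells, which are not available here.
- **Nothing is tested in the split, and the endpoint is exploratory.** This stands, so the risk is misreading, not type I error. In 8.3.2 and 8.4.1.2 the randomised-arm MMRM can fairly be called a sensitivity analysis; only in 8.2.2 does the split stand alone.
- **The sizes are assumed.** This stands. Blocking is at the Investigator's discretion. Entry requires 1 to 10 crises in the previous 12 months, which trims both tails, so variance 1 may be high.
- **The rate is not singled out.** Time to first VOC also has only a P-value between arms, and a between-arm VOC estimate with CIs exists for the proportion. This stands; the missing rate estimate is a gap, not an anomaly.
- **The 73-per-year case barely touches the Wilcoxon test.** Correct: it is merely a top rank. A reader might infer that short dosing invalidates the test; only the descriptive mean is affected.
- **Splitting placebo by sham step would not cure the problem.** This stands. About 0.3-0.5 of 12 PBO2 participants would be expected at the lowest step. With active-only titration failure of 10-20% per visit and no drug effect on VOCs, the top-step active/placebo ratio still runs from 0.64 to 1.21.

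These points limit the weight of the concern. They do not make a split on a post-randomisation variable a sensitivity analysis.

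**Conclusion.** Minor, on two counts. First, the by-step tables are mislabelled and lack their reference columns. With no drug effect, selection alone could put the 18 mg column 6-14% below its own arm (equal underlying rates) or 8-23% below (variance 1). This assumes 2-4 VOCs/year, a VOC in the preceding 5-7 days blocking uptitration 50-80% of the time, and no VOC ending dosing. A reader might infer that a false dose trend is certain; the documents do not support that, since the gradient may be absent or reversed.

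Second, SAP 8.2.1 gives no between-arm estimate with a CI for the VOC rate, and neither the per-person mean nor the median is a dependable substitute. The primary endpoint, TEAEs, is not involved.

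The grouping rule also leaves cases open. Protocol 3.5.4.3 says that participants who do not tolerate the initial dose "should be reduced to a 3-mg QD dose (ie, reduction by 1 tablet"). Those who stay there could be counted as 6 mg, because they never up-titrated, or have no column. Someone reduced from 18 to 12 mg still counts as 18 mg by last up-titration.

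**What to change.** 1. In SAP 8.2.2, 8.3.2 and 8.4.1.2, retitle the split as a descriptive summary by dose step reached. Place the whole randomised 18 mg arm and whole PBO2 beside it. Add a footnote: the groups are formed after randomisation, differences between them are not randomised comparisons, and they do not test the robustness of the main analysis. State how participants reduced to 3 mg, or reduced after an uptitration, are classified in the table. A PBO2 split by sham step is optional only.
2. In SAP 8.2.1, keep the Wilcoxon test. Add total VOCs divided by total patient-years by randomised arm, with the same first-to-last-dose window for events and exposure (SAP 7.1 already derives patient-years). Add an HU-adjusted rate ratio with 95% CI from a count model with log dosing time as offset and an allowance for overdispersion. In simulated null trials, type I error was 3.1-10.3% for Poisson without the allowance, 2.6-4.8% with deviance scaling and 2.3-3.9% with Pearson scaling. If an arm has no VOC, report the rates only.

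The cost is SAP wording and a little programming on data already collected. The main drawback is a wide interval, with limits about a factor of 2 to 3.4 either side of the estimate under the assumed rates.
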